Sub Aim 2a) Compare the two interventions on rate of self-reported MRSA SSTI recurrence and repeat surgery over a 12 month follow-up period.

Sub Aim 2b) Compare the two interventions on patient-centered outcomes such as quality of life and school attendance as well as others informed by Aim 1 over a 12 months follow-up period.

Sub Aim 2c) Determine the burden and patient preferences regarding the decolonization protocol on families.

The proposed research will be conducted as a randomized controlled comparative effectiveness trial over three years. Aim 1 will be carried out over a six months period. For Aim 2, recruitment and randomization will be done over a period of approximately 12 months and will be followed by a 12 month long evaluation period. Interviews as well as recruitment and randomization will be carried out in the pediatric surgery outpatient clinic and over the phone for patients of the Emergency Department at Riley Hospital for Children in Indianapolis, IN. Evaluation will be done by trained research assistants through phone interviews (or data collection via US post and/or online via secure email link to REDCap) at approximately 6 weeks, 6 months, and 12 months.

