At the time of enrollment, those randomized to intervention 1 will receive written hygiene instructions and a form to document outcomes, such as missed school or work. Those randomized to (or placed in) intervention 2 will receive a "kit", which will include a bucket for measuring the water, two cups to be used for measuring bleach, Clorox bleach, mupirocin ointment, double sided q-tips for application of mupirocin, hygiene instructions, as well as a form to document outcomes. Participants will also receive a link to an online video demonstrating the accurate process for preparing the diluted bleach bath and administering the mupirocin. (www.youtube.com/watch?v=3RbtyLT071M&feature=youtu.be) For each intervention arm, the above materials will be sent via mail after enrollment or provided in person by a research assistant.

Outcomes Measures

The patient-centered outcomes we plan to measure are summarized below.

The results of PAB sessions performed during aim 1 of this study will further inform some of the patient-centered outcomes measures.

Recurrence of SSTI

 Percent of participants with recurrence of skin and soft tissue infection by parental report at 6 weeks, 6 months and 12 months.
Repeat surgery

 Percent of participants with repeat incision and drainage procedure by parental report at 6 weeks, 6 months and 12 months.
Adherence to intervention

 Participant adherence to intervention measured on a 5 point scale by parental report at 6 weeks Household adherence measured on a 5 point scale by parental report at 6 weeks Have you tried anything outside the protocol to reduce the risk of MRSA recurrence? If yes, then what? (6 weeks)
Side effects
Percent of participants with side effects from intervention by parental report at 6 weeks and 6 months.
Participant time committed to intervention
Estimated weekly time to adhere to intervention by parental report at 6 weeks
Quality of Life

 Participants' quality of life measured by parent-proxy report (or youth tool) of the PedsQL 4.0 (Pediatric Quality of Life Inventory) at recruitment, 6 weeks, 6 months, and 12 months. Impact on free time measured on a 5 point scale by participant (age\geq13) and parental report at 6 weeks
Impact on school attendance

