
 Participants' school attendance by parental report at 6 weeks, 6 months and 12 months
Impact on parents' work attendance

 Assessment of parents' work attendance by self report at 6 weeks, 6 months and 12 months
Other Patient Centered Outcomes

 Participant's level of pain and discomfort at incision site via NRS at enrollment and 6 weeks. Participant's level of knowledge on what MRSA is and how to prevent its recurrence at enrollment, 6 weeks, 6 months, and 12 months. Additional measures as suggested by Aim 1

Data Collection and Study Tools

In order to evaluate the outcomes identified above, data will be collected by RAs in person or by phone at enrollment, and through phone interviews at approximately 6 weeks, 6 months and 12 months as time allows within the study period. RAs will be trained to perform phone interviews to assess recurrence, adherence, side effects, quality of life and school/work attendance. When requested by the participant, data collection tools/questions may be mailed via US post and/or emailed via secure link to REDCap. For all practical outcomes, such as missed school and work, participants will have forms to help them document these outcomes to aid in recollection at follow up.

The data collection for specific outcomes is outlined below:

Recurrence of skin and soft tissue infection

An RA will contact a parent of participants by phone at approximately 6 weeks, 6 months and 12 months. Participants will be asked whether they have had a recurrence of MRSA SSTI since the previous contact. If the answer is yes, they will also be asked if and where medical care was sought, and if any interventions (surgery, antibiotics) were needed. In cases for which antibiotics were prescribed, the name of antibiotics and duration of course will be recorded.

Repeat surgery

In a continuation of the questioning as shown above, an RA will contact a parent of participants by phone at approximately 6 weeks, 6 months and 12 months. They will be asked whether participants needed another incision and drainage procedure for MRSA SSTI in the same or another body location. If the answer is yes, they will also be asked in what facility that was done and whether antibiotics was prescribed or not. In the cases for which antibiotics were prescribed, the name of antibiotics and duration of course will be recorded.

Adherence to intervention

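### Reported recurrence rests on an unconfirmed answer from a parent who knows the arm; pre-specify medically treated recurrence, from answers already collected, as a supportive outcome

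*Combined protocol and SAP*

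**What the plan says.** Section 2.0, Sub Aim 2a, compares the arms on the "rate of self-reported MRSA SSTI recurrence and repeat surgery over a 12 month follow-up period". The outcome list in Section 5.0 defines recurrence as "Percent of participants with recurrence of skin and soft tissue infection by parental report at 6 weeks, 6 months and 12 months". The data-collection text gives the question: "Participants will be asked whether they have had a recurrence of MRSA SSTI since the previous contact". It supplies no case definition, culture, examination or adjudication.

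After a yes, the parent is asked whether and where care was sought and whether surgery or antibiotics were needed ("they will also be asked if and where medical care was sought, and if any interventions (surgery, antibiotics) were needed"). The name and duration of any antibiotic are recorded.

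Repeat drainage has its own entry in the list: "Percent of participants with repeat incision and drainage procedure by parental report at 6 weeks, 6 months and 12 months". It is collected in the same interview, with the facility noted, and Sub Aim 2a compares it by arm.

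Section 5.0 also permits medical record review for items the parent cannot supply, such as where a recurrence was located. The review is optional and is not described as confirming a reported recurrence.

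Section 8.0 contains only the sample-size calculation. It names no test, supportive outcome or sensitivity analysis.

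**The concern.** No masking is described. One arm receives bleach, mupirocin and a measuring bucket; the other receives written hygiene advice. That the reporting parent knows the arm is an inference from the interventions, but a safe one. Masking the interviewer would not change it.

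Reported recurrence gives the same weight to a minor lesion no clinician saw and to a treated abscess. A family that has completed six weeks of baths may be slower to call a small lesion a recurrence, or a hygiene-only family quicker. Either tendency would favour decolonization without any difference in infection. With reported recurrence alone, fewer infections and fewer reports look the same.

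Repeat drainage gives a harder comparison, but a narrow one, since it leaves out every recurrence managed with antibiotics only. The answers that would capture those are collected and then assigned to no outcome. Pre-specification matters because a definition of treated recurrence chosen after the results are known would carry little weight.

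**Working it through.** **The plan's own figure.** Section 8.0 gives 50% recurrence under hygiene education, a 50% relative reduction (so 25%), alpha 0.05 and power 0.80 (printed there as beta). With the mean risk (0.50 + 0.25)/2 = 0.375 and two-sided alpha:

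n = 2 × (1.960 + 0.842)² × 0.375 × 0.625 / 0.25² = 58.87, rounded up to 59 per group.

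This matches the plan. Full binomial enumeration of the pooled two-sided z-test at 59 v 59 gives 80.9% power for 50% v 25%.

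**Assumptions.** The documents give no reporting-error rates and no share of recurrences that are treated. All such rates below are assumed.

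**Over-reporting with no true effect.** Reported risk = true risk + (1 − true risk) × false-report rate. True recurrence is 40% in both arms. Decolonization families falsely report at 5%, so their reported risk is 0.40 + 0.60 × 0.05 = 43%.

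| False-report rate, hygiene | Reported risk, hygiene v decolonization | Two-sided false-positive rate |
|---|---|---|
| 10% | 46% v 43% | 6.4% |
| 15% | 49% v 43% | 10.3% |
| 20% | 52% v 43% | 17.0% |

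With true recurrence of 30% and rates of 20% v 5%, the reported risks are 44% v 33.5% and the rate is 21.3%.

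**Under-reporting with no true effect.** If true recurrence is 50% in both arms and decolonization families fail to report 20% of it, the reported risks are 50% v 40% and the false-positive rate is about 20%.

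**Does treated recurrence protect?** Treated risk = true risk × share treated + (1 − true risk) × false-report rate × share of false reports treated. For the 20% v 5% case with true recurrence of 40%:

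| Share of false reports treated | 80% of true recurrences treated | 60% of true recurrences treated |
|---|---|---|
| None | 32% v 32%: 5.1% | 24% v 24%: 5.2% |
| Half | 38% v 33.5%: 7.9% | 30% v 25.5%: 8.7% |
| All | 44% v 35%: 16.8% | 36% v 27%: 18.6% |

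The protection is complete only in the first row and is lost in the last.

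**Cost in power.** Under the planned effect with accurate reporting:

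- 80% treated: 0.8 × 50% v 0.8 × 25% = 40% v 20%, power 67.4%.
- 60% treated: 0.6 × 50% v 0.6 × 25% = 30% v 15%, power 51.1%.

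**Risk of a significance-based rule.** Simulating a genuine 50% v 25% effect, with treated recurrences a subset of reported ones: among trials significant on reported recurrence, the treated comparison is non-significant in about 20% (80% treated) or 39% (60% treated).

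**The case against.** Self-report is a declared choice in a patient-centred comparative effectiveness trial. The families have already been through a culture-confirmed, drained abscess, so they may judge recurrence well. The reporting rates above are invented, and the mildest case barely moves the error rate (6.4%). This stands: the documents hold no evidence that reporting will differ by arm, and the figures show only what could happen.

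A reader might infer that the plan has no harder comparison, or that the surgery answers go unused. The documents do not support that. Repeat incision and drainage is a listed outcome at all three contacts and is compared by arm. What goes unused is the care-sought and antibiotic answers.

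A reader might also infer that treated recurrence would settle the question. It would not. It comes from the same parent and is asked only after a yes, so a treated episode that is never reported stays invisible. Parents decide whether to seek care, and a clinician told about decolonization may prescribe differently. The near-5% error rate follows from assuming that false reports are untreated.

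Finally, it is tempting to read a benefit in reported recurrence without a significant benefit in treated recurrence as a sign of biased reporting. At this sample size that would put a false flag on a sizeable share of genuine effects.

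**Conclusion.** The point holds as a worthwhile, inexpensive improvement, not as a flaw that invalidates the outcome. The outcome on which the trial is sized is an unconfirmed report by a parent who, given the interventions, knows the arm. Repeat drainage is a partial check only, and the optional record review is not presented as confirmation.

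Under the assumed over-reporting, the two-sided false-positive rate is 6% to 17% in place of 5%. A treated-recurrence comparison would stay near 5% if false reports go untreated, and would be about 8% to 9% in the 20% v 5% case if half are treated. It addresses over-labelling of minor lesions. It does not address treated episodes that parents leave out. With power of about 67% or 51%, it can support the main outcome but not replace it.

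**What to change.** Keep parent-reported recurrence as the main outcome. Add to the outcome list and to Section 8.0:

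1. **Definition.** Medically treated recurrence: a reported recurrence for which antibiotics were prescribed or drainage was performed.
2. **Analysis.** By randomized arm at 12 months, with the same method as reported recurrence. Give the risk difference and risk ratio with 95% confidence intervals beside those for reported recurrence, plus the share of reported recurrences that were treated, by arm.
3. **Interpretation.** Compare the size and direction of the two estimates. Do not make the reading depend on whether the supportive one is significant.
4. **Limits.** State that the informant is the same, that the treatment questions follow only a yes, and that care-seeking may itself differ by arm.

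The cost is one outcome definition and one extra analysis from answers already collected, with no new visits or participants. The downside is fewer events and lower power for the supportive outcome.

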The interventions will be targeted to all household members for whom consent can be obtained. All participants will receive written instructions for the intervention to which they are randomized. A registered nurse in the pediatric surgery clinic will be available to review instructions and answer any questions about MRSA. The instructions for the diluted bleach bath and Mupirocin administration will also be publically available in an online video.

Intervention number 1, Hygiene education

Participants will receive specific hygiene instructions according to existing recommendations from the Ryan White Center for Pediatric Infectious Disease, Riley Hospital as outlined here:

- Take daily showers or bath with soap
- Clean hands with soap and water or with hand sanitizers when hands are dirty, and after each bathroom break or diaper change
- Don't share towels, wash cloths, clothing, toothbrushes, or razors within the family or with friends
- Discard lotions in jars (can be easily contaminated with MRSA when someone puts their hand in a jar)
- Keep all wounds including cuts and scrapes clean and covered until healed
- Avoid other person's dirty bandages or uncovered wounds
- Encourage athletes or health club members to shower before and after all practices and competitions, and wipe down equipment surfaces before and after use
- Uniforms and practice jerseys should be washed after each game or practice. Sports equipment should be washed/cleaned weekly
- Wash all towels, wash cloths, sleepwear, underwear, and linens in hot water with laundry detergent once weekly and dry with hot air in a dryer

Intervention number 2, Hygiene education and Decolonization

Participants in this intervention group will receive the same hygiene instructions as the participants in the first intervention group. In addition, intervention number 2 will include the following for all consented household members:

- Twice weekly 15 minute soaks in diluted bleach water (a cup of 6% sodium hypochlorite [Clorox; The Clorox Company] for a standard 50 gallon tub of water, or a teaspoon for each gallon of water used) for the duration of 6 weeks
- Application of 2% mupirocin ointment by the use of clean swab to the bilateral anterior nares twice daily for ten days

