An RA will contact a parent of participants by phone at approximately 6 weeks after study randomization. The RA will ask parents of participants about adherence to interventions. The RA will initiate the conversations by saying “we are very interested to know what people think about the protocol”. For any of the interventions experienced (hygiene measures, mupirocin to nose, and bleach bath) participants will then be asked to report adherence. Adherence will be reported on a 5 point scale for child and other family members: We followed the instructions as recommended – always, sometimes, never.

For the purpose of analysis “always”, “never omitted more than one time/dose/bath in a row” and “never omitted more than one day/week in a row” will be considered adherent to treatment.

RAs will also ask: “Have you tried anything outside the protocol to reduce the risk of MRSA recurrence? If yes, then what?” This should capture any patients in the control arm who may be using decolonization regimens outside their designed protocol.

Side effects

An RA will contact a parent of participants by phone at approximately 6 weeks after randomization. The RA will ask parents of participants about side effects to interventions, for example: “Did any family member experience side-effects from the intervention? All parents will also be asked: “Dry skin and irritation in the nose or runny nose are sometimes reported in families, have any of your family members experienced those symptoms?”

Participant time committed to intervention

An RA will contact a parent of participants by phone at approximately 6 weeks after randomization. If participant report that they adhere to the protocol, the RA will ask parents to estimate the amount of time (in hours) per week they estimate the intervention took for all family members combined.

Quality of Life

Impact on quality of life will be measured by the use of Peds QL, Pediatric Quality of Life Inventory.²² The Peds QL was developed to measure health-related quality of life (HRQOL) in healthy children and adolescents and those with acute and chronic health conditions. The RA will administer the 23-item parent proxy report of the Pediatric Quality of Life Inventory in person or by phone at recruitment and at recruitment, and over the phone at approximately 6 weeks, 6 months, and 12 months. Participants 13 and older will be able to give self-report.

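### The adherence rule limits only consecutive omissions, so it can class 6 of 12 baths as adherent and 8 of 12 as non-adherent, and its categories do not match the answers listed

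*Combined protocol and SAP*

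**What the plan says.** All references are to section 5.0 of the combined protocol and SAP unless stated.

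- **Schedule (Intervention number 2).** Baths are "Twice weekly 15 minute soaks in diluted bleach water", "for the duration of 6 weeks". Mupirocin is applied "to the bilateral anterior nares twice daily for ten days".
- **Analysis rule (Adherence to intervention).** Three categories "will be considered adherent to treatment": *always*, "never omitted more than one time/dose/bath in a row" and "never omitted more than one day/week in a row".
- **Answers.** The same subsection describes a five-point scale, for the child and for other family members, but lists only three answers: *always*, *sometimes* and *never*. Parents are asked about each component they experienced (hygiene measures, mupirocin, bleach bath).
- **Place in the plan.** Outcomes Measures lists participant and household adherence at 6 weeks. No count of baths or applications taken is described, and no minimum share is set.

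**The concern.** Two of the three qualifying categories restrict only how many omissions may follow one another. Neither caps the total, so a family that regularly skips every second bath or dose satisfies the rule for the whole course. A family with one longer gap and otherwise complete treatment may not, even though it received more of the regimen. The resulting percentage adherent would be hard to interpret.

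This matters most if recurrence does not differ between arms. Readers will then ask whether decolonization did not work or was not carried out. A single adherent class that covers anything from half to all of the schedule cannot separate these explanations. The plan also describes no count from which exposure could be rebuilt afterwards.

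A second problem is that the categories used for analysis are not among the answers listed for the interview, so the plan does not show how one is derived from the other.

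**Working it through.** The plan states no adherence figure, so there is none to reproduce. The check asks what the rule admits.

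**Inputs (Intervention number 2)**
- Baths: 2 per week × 6 weeks = 12 per person.
- Mupirocin: 2 per day × 10 days = 20 applications per person.

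**Lowest exposure under the gap-based categories.** Split n scheduled occasions (n even) into n/2 successive pairs. If no two omissions are adjacent, each pair contains at least one occasion taken, so at least n/2 are taken. Strict alternation achieves exactly n/2.
- By bath: 12/2 = 6 of 12 (50%).
- By application: 20/2 = 10 of 20 (50%).
- By week: 6/2 = 3 weeks kept × 2 baths = 6 of 12 (50%).
- By day: 10/2 = 5 days kept × 2 applications = 10 of 20 (50%).

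The week and day lines assume that *week* refers to baths, *day* to mupirocin, and that every week or day not skipped is complete.

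**Does the rule follow total exposure?**

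| Pattern | Taken | Share | Longest gap | Class |
|---|---|---|---|---|
| Every second bath omitted | 6/12 | 50% | 1 bath | adherent |
| Every second week omitted | 6/12 | 50% | 1 week | adherent |
| Two whole weeks in a row omitted, rest complete | (12 − 4)/12 = 8/12 | 67% | 4 baths, 2 weeks | non-adherent |
| Every second application omitted | 10/20 | 50% | 1 application | adherent |
| Every second day omitted | 10/20 | 50% | 1 day | adherent |
| Two whole days in a row omitted, rest complete | (20 − 4)/20 = 16/20 | 80% | 4 applications, 2 days | non-adherent |

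The third and sixth patterns fail both gap-based categories and are not *always*. No single threshold on the share completed could put 6/12 on the adherent side and 8/12 on the other, or 10/20 and 16/20 likewise. The rule is therefore more than a lenient cut-off on exposure.

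**Answers against categories.** The three listed answers and the two gap-based phrases share only *always*. If the phrases are offered as answers, a family skipping every second bath would correctly choose the first and be classed adherent. If they are not offered, the same family might say *sometimes*, and the plan does not show how the two gap-based categories would be filled.

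**The case against.** **The 50% is an extreme.** This stands. It is the floor of a class running from 50% to 100%, and nothing in the documents suggests how often families would alternate strictly. A reader might infer that the trial will report half the regimen as adherence; the documents support only that it can.

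**The scale is not shown.** This stands too. Three listed answers plus two gap-based phrases make five, so it is tempting to say that three of five answers count as adherent. The document never lists five answers, and an alternate-skipper who answers *sometimes* would not be counted. This makes the misclassification conditional and adds the mismatch as a defect of its own.

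**There is no reference standard, so this is just a cut-off.** The documents define no correct level of adherence, and none is proposed here. But the rule can rank lower exposure above higher, which is not a question of where to set a threshold.

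**The detail is collected anyway.** This stands in part. If the gap-based phrases are answers, the categories can be reported separately by component at no cost. Even then, they do not give the amount taken.

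**Burden is not shown to be biased.** A reader might infer that the weekly-time estimate would mix full- and half-regimen families and so understate burden under Sub Aim 2c. The text says "If participant report that they adhere to the protocol, the RA will ask parents to estimate the amount of time", which depends on what the parent reports and is not tied to the analysis rule. Outcomes Measures lists the time estimate with no such condition, and Sub Aim 2c does not name adherence. That inference is not relied on.

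**Conclusion.** The point holds as a statement of what the rule permits. A family can be classed as adherent at 6 of 12 baths or 10 of 20 applications, while 8 of 12 baths with two whole weeks missed in a row, or 16 of 20 applications with two whole days missed in a row, is non-adherent. Separately, the analysis categories and the listed answers do not agree.

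The consequence is limited to a listed secondary outcome and to the interpretation of a null recurrence result. Section 8.0 specifies no per-protocol or adherence-adjusted analysis, so it would be wrong to infer that the recurrence comparison or the 59 per group is affected.

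The figures rest on the schedule as written and on reading a skipped week or day as wholly missed and a kept one as complete. The document does not say how a partly kept week is classed. A looser reading could admit less than 50%, but the text does not establish it and the conclusion does not need it.

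**What to change.** 1. Reconcile the answers read to parents with the analysis categories: list all five points of the scale and state which category each one feeds.
2. Report each category separately for bleach bath, mupirocin and hygiene, instead of collapsing the top three into one adherent class. If the five points are already recorded, this costs nothing.
3. On the existing 6-week call, record for the index child the baths taken out of 12 and the approximate mupirocin applications out of 20. Report the proportion of the schedule completed. If the investigators want a threshold, they should state it in advance; none is proposed here. Hygiene items can stay as categories.

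**Cost.** The two counts add a little interview time and rely on parental recall. Recall will be weaker for mupirocin: a ten-day course started at randomization ends about 42 − 10 = 32 days before a 6-week call, so that count should be labelled approximate. A tick-box diary would help recall, but it would be used in one arm only and could itself change adherence, so it should be optional.

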5.0 Study Procedures

AIM 1. Explore MRSA abscess outcomes important to patients and their families through a Patient Advisory Board (PAB) and incorporate results in outcomes tools to be used in the randomized comparative effectiveness trial

In order to ensure we are measuring outcomes that are important to patients and their parents we will invite families who have experienced an incision and drainage procedure in the pediatric surgery clinic or Emergency Department to participate in a Patient Advisory Board (PAB) for the study. The Patient Advisory Board meetings will consist of informal and interactive discussions facilitated by design researchers. The meetings will allow participants to contribute as much or as little as they feel comfortable doing. One Patient Advisory Board will be comprised of parents or legal guardians of children ages 3 months to 8 years old who have undergone an incision and drainage procedure at Riley for an abscess. The other Patient Advisory Board will be made up of children 9-18 years old who have undergone an incision and drainage procedure at Riley for an abscess and their parents or legal guardians. The meetings will last up to 4 hours and will focus on study acceptability, recruitment, and patient centered outcomes. Participants will be compensated for their contribution to the study with a \$20 per hour payment in the form of a gift card. No more than two family members will be compensated for participation, e.g. one parent and one child who participate can each be paid \$20 per hour or two parents who participate can each be paid \$20 per hour. The Patient Advisory Board may also reconvene if additional patient input is needed during the study.

AIM 2: Compare strategies of care for MRSA SSTI, specifically abscess surgery and hygiene education versus abscess surgery and hygiene education followed by decolonization, on outcomes such as SSTI recurrence and repeated surgery, and patient-centered outcomes such as quality of life, side-effects and school absence

This part of our study is a randomized comparative effectiveness trial. Recruitment, randomization, and collection of outcomes will be done by PResNet.

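### The side-effect outcome counts what unmasked parents attribute to the regimen, so the arms can differ with no true difference; the any-cause symptom question already put to all parents should be the named comparison

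*Combined protocol and SAP*

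**What the plan says.** The outcome list in section 5.0 (Outcomes Measures, Side effects) defines the measure as "Percent of participants with side effects from intervention by parental report at 6 weeks and 6 months". The Aim 2 heading in the same section includes "patient-centered outcomes such as quality of life, side-effects and school absence" among the outcomes used to compare the two strategies, so this percentage is a between-arm contrast.

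The data-collection paragraph on side effects, also in 5.0, describes a call to a parent about 6 weeks after randomization, with two questions:

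- The first, offered as an example, is "Did any family member experience side-effects from the intervention". The parent must judge cause.
- The second is introduced by "All parents will also be asked" and reads "Dry skin and irritation in the nose or runny nose are sometimes reported in families, have any of your family members experienced those symptoms". It asks nothing about cause and sets no start date. Like the first, it covers the whole family.

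Both arms receive hygiene instructions, which include "Take daily showers or bath with soap" and hand sanitizer. The decolonization arm adds diluted bleach soaks and "Application of 2% mupirocin ointment by the use of clean swab to the bilateral anterior nares twice daily for ten days", supplied as a kit. No masking of parents is described. Section 8.0 covers only the sample size for recurrence. It gives no analysis of side effects, and no section says which question produces the reported percentage.

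**The concern.** A percentage that depends on perceived cause combines how often symptoms occur with how readily a parent links them to the regimen. The second component can differ by arm in an open trial. A parent applying ointment inside the nose has an obvious explanation for a runny or irritated nose; a parent given a hygiene sheet does not. For dry skin the gap may be smaller, because frequent washing and sanitizer can also be blamed.

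Sub Aim 2c sets out to determine the burden of decolonization on families, and tolerability is part of that. If the attributed percentage is reported as the arm comparison, a reader cannot tell excess symptoms from excess attribution. Because the plan does not fix which question is the outcome, that choice could also be made after the data are seen.

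**Working it through.** **The plan's own figure.** None is stated for side effects. The only design figure is 59 per group for recurrence (8.0). With 50% v 25%, mean 0.375, two-sided α 0.05 and power 0.80, 2(1.96 + 0.842)² × 0.375 × 0.625 / 0.25² = 58.87, which rounds up to 59. It reproduces but does not bear on this point. It helps only in reading the enrollment target of 95 as per arm: 95 × 0.8 × 0.9 × 0.9 = 61.6, just above 59. On that reading 95 × 0.8 = 76 families per arm are reachable at 6 weeks.

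**Attributed question, no true difference.** Let s be the symptom rate, equal in both arms, and a₁ and a₀ the share of symptomatic families who blame the intervention (decolonization, hygiene). The reported difference is s(a₁ − a₀). All rates here are assumed.

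| s | 50% v 10% | significant | 50% v 25% | significant |
|---|---|---|---|---|
| 10% | 5% v 1%: 4 points | 30% | 5% v 2.5%: 2.5 points | 12% |
| 20% | 10% v 2%: 8 points | 55% | 10% v 5%: 5 points | 21% |
| 30% | 15% v 3%: 12 points | 74% | 15% v 7.5%: 7.5 points | 31% |
| 40% | 20% v 4%: 16 points | 87% | 20% v 10%: 10 points | 41% |

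With a₁ = a₀ the difference is zero. The significant columns give the approximate share of trials with p < 0.05 at 76 per arm, by normal approximation. The first row is rough, since 76 × 0.05 = 3.8 and 76 × 0.01 = 0.8 expected events.

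**Attributed question, with a true excess.** With background b and a true excess of d points, the attributed difference is a₁(b + d) − a₀b. At 50% v 10% this is 0.4b + 0.5d, which exceeds d only when b > 1.25d. For d = 20 points, b = 10% gives 4 + 10 = 14 (too small) and b = 40% gives 16 + 10 = 26 (too large). The error can go either way.

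**Prompted question, any cause.** Suppose background b is equal in both arms and the regimen independently causes symptoms with probability e. The rates are b and b + (1 − b)e, so the difference is (1 − b)e. For e = 20 points and b = 10%, 20%, 30% and 50%, the observed difference is 18, 16, 14 and 10 points, with power of about 81%, 60%, 43% and 23% at 76 per arm. This is dilution; no difference appears when e = 0.

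**Unit of count.** The outcome is per participant, but both questions ask about any family member. If each of four members independently has background probability 10%, 20% or 30%, the chance of at least one symptomatic member is 1 − (1 − p)⁴ = 34%, 59% or 76%. A family-level answer is not the listed percentage.

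**Timing.** The outcome list gives 6 weeks and 6 months. The side-effects paragraph describes only the 6-week call. The general data-collection text names side effects among the interview topics, but no 6-month wording or window is given.

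**The case against.** The strongest reply is that the plan already asks every parent the same symptom question without asking cause. That stands. A reader might infer that the side-effect data rest wholly on blame, and the documents do not support that. What remains is that the listed outcome is nonetheless worded as attributed, and the neutral question is neither windowed nor named as the outcome.

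A reader might also infer that undated background symptoms make the comparison unfair. Among randomized families they fall on both arms alike and only shrink a real difference. Bias on that question would need arm-dependent recall or reporting, which is possible in an open trial but is a separate argument. The families whom section 4.0 allows to be placed in the decolonization arm are outside this protection.

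Other stronger readings also fail:

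- Hygiene parents do have something to blame for dry skin.
- The attributed figure need not overstate the excess, as the working shows.
- A family-level background of 34–76% is not a ceiling that would hide an effect.
- The text calls the symptoms sometimes reported, not common, and nowhere says that the two questions will be pooled.

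Finally, parent-perceived side effects are a legitimate measure of burden under Sub Aim 2c. That supports keeping the attributed item as description, not as the arm comparison.

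**Conclusion.** The point holds in this limited form. The stated side-effect outcome is an attributed percentage from unmasked parents, used to compare arms of which only one receives bleach and a nasal product. It can show a difference where there is none. The size cannot be derived from the documents: it is 4–16 points on the wider assumed attribution gap, 2.5–10 on the milder one, and zero if attribution is equal, for assumed true symptom rates of 10–40%. Neither the direction nor the size of error is established for this trial when there is a true excess. The recurrence comparison is unaffected. This is an inexpensive improvement to a secondary comparison, most of whose data are already planned for collection.

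**What to change.** - Name the between-arm side-effect outcome as the prompted symptoms from any cause, new since enrollment, with dry skin, nose irritation and runny nose recorded separately.
- Ask for the index child separately from other household members, so that the child's answer matches the per-participant definition.
- Report the risk difference against the hygiene arm with its confidence interval for each symptom.
- Keep the parent's attribution as a descriptive item by arm, and do not pool it with the prompted item.
- Reconcile the 6-month time point in the outcome list with the 6-week call in the side-effects paragraph. If 6 months is kept, state its question and window.

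The cost is a few words in the call script, a few more recorded fields and one analysis line, with no extra contact. The price is some dilution by background symptoms. Reporting by parents who know their arm remains a limitation.
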